Visits' Activities/ Assessments	¹ Screenin g ^b	C	C O		C1		C2	C3	C4	C5 to C12	C13 to C24	C>24 ^c	EoT ^d	30-day Safety Follow-up (Adult and Paediatric) ^e	Long-term Post-treatment safety Follow-up (Paediatric Only) ^f	Details in section
Day of each cycle	-28 to -1	1	2	1	8	28	28	28	28	28	28	28	NA	NA	NA	
Study day	-28 to -1	1	2	3	10	30	58	86	114	142 to 338	366 to 674	>674	NA	EoT + 30 days	Up to EoT + 1 year	
Visit window (days)		0	0	0	0	±7	±7	±7	±7	±7	±7	±7	NA	+7	±7	
Efficacy measurements	5															
Tumour assessments ^t	X								Х	X	Х	Х	Х			Section 8.1.1
Disfigurement ^u	X									X	Х					Section 8.1.2
Clinical outcome assess	sments															
FLACC pain scale (3 years only) ^v		Х				X	Х	X	X	X	X	Х	Х			Section 8.1.3.1.1
Faces pain scale - revised (4 to 17 years only) ^v		Х				Х	Х	Х	X	X	X	Х	Х			Section 8.1.3.1.2
NRS-11 (adult cohort) ^v		Х				X	Х	Х	Х	Х	Х	Х	Х			Section 8.1.3.1.3
PII ^{v,w}		Х				Х	Х	Х	X	Х	Х	Х	Х			Section 8.1.3.1.4
Pain medication survey ^v		Х				X	Х	Х	X	Х	Х	Х	Х			Section 8.1.3.1.5
PedsQL (paediatric cohort) ^{v,x}		Х				X	Х	Х	X	Х	Х	Х	Х			Section 8.1.3.2.1
EORTC QLQ-C30 (adult cohort) ^v		Х				Х	Х	X	X	Х	X	Х	Х			Section 8.1.3.2.2

CONFIDENTIAL AND PROPRIETARY

Visits ^a Activities Assessments	Screenin g ^b	C	0		C1		C2	C3	C4	C5 to C12	C13 to C24	C>24 ^c	EoT ^d	30-day Safety Follow-up (Adult and Paediatric) ^e	Long-term Post-treatment safety Follow-up (Paediatric Only) ^f	Details in section
Day of each cycle	-28 to -1	1	2	1	8	28	28	28	28	28	28	28	NA	NA	NA	
Study day	-28 to -1	1	2	3	10	30	58	86	114	142 to 338	366 to 674	>674	NA	EoT + 30 days	Up to EoT + 1 year	
Visit window (days)		0	0	0	0	±7	±7	±7	±7	±7	±7	±7	NA	+7	±7	
PlexiQoL (adult cohort) ^v		Х				X	Х	Х	X	Х	Х	Х	Х			Section 8.1.3.2.2
Physical functioning (PROMIS) ^{v,y}		Х				X	Х	Х	X	Х	Х	Х	Х			Section 8.1.3.3
PGIS ^{v,z}		Х				Х	Х	X	Х	X	Х	Х	Х			Section 8.1.3.4
PGIC ^{v,z}						Х	Х	Х	Х	Х	Х	Х	Х			Section 8.1.3.5
Pharmacokinetic measu	rements															
PK blood samples ^g		X	Х		Х											Section 8.5
Study treatment admini	istration									·						
Dispense/return of selumetinib ^{aa}		X		Х		X	Х	X	X	X	X	Х				Section 6
Study treatment compliance ^{bb}		Х		Х		X	Х	Х	X	X	Х	Х				Section 6.4

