- ^t Tumour assessments will be performed at screening and every 4 cycles (16±1 weeks) up to the end of Cycle 24 (i.e. at the end of Cycles 4, 8, 12, 16, 20, and 24). From the end of Cycle 24, tumour assessments will be performed every 6 cycles (24±1 weeks) as long as the subject remains on study treatment or until disease progression. Subjects who discontinue study treatment due to reasons other than disease progression will continue to undergo tumour assessments for approximately 1 year, if clinically applicable, and the assessment schedule should continue per the regular tumour assessment interval.
- ^u Disfigurement assessments will be performed at screening and at the end of Cycles 8, 16 and 24 as long as the subject remains on study treatment.
- ^v Baseline clinical outcome assessments should be performed prior to and as close to the first dose of selumetinib as possible (PGIC should not have any baseline assessments). Post-baseline assessments should be performed at the end of each cycle up to the end of Cycle 4, every 2 cycles up to the end of Cycle 12, every 4 cycles up to the end of Cycle 24, and every 6 cycles thereafter, as long as the subject remains on study treatment. In the pediatric cohort, the pain medication survey will be completed on paper by the parent. In the adult cohort, the pain medication survey will be completed on paper by the patients. Other assessments will be performed electronically using on-site tablets.

- * Adults and children from 8 to 17 years of age will complete self-reported PII; parents/legal guardian of children from 5 to 17 years of age will complete the parent proxy PII.
- Subject-reported versions are for subjects aged 5 to 7 years, 8 to 12 years, and 13 to 17 years. In addition, the corresponding parent-reported versions will also be included. For subjects 3 to 4 years of age, only the parent-reported version will be included.
- ^y Self-reported short forms will be administered to children from 8 to 17 years of age and parallel parent proxy forms to children aged from 5 to 17 years. In the adult cohort, a newly developed PROMIS short form physical functioning scale will be used.
- ^z Will be parent-reported for children aged up to 17 years and self-reported for children aged 8 to 17 years and adults.

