6.3 Measures to minimise bias: randomisation and blinding

6.3.1 Subject enrolment and randomisation

This is an open label Phase 1 study to assess the safety, tolerability, PK, and clinical efficacy of selumetinib in Chinese paediatric and adult subjects with NF1 and inoperable PN. Randomisation will not be performed in this open label study. Approximately 16 paediatric and 16 adult subjects with NF1 and inoperable PN will be enrolled in the study. Enrolment and treatment assignment will be performed using Interactive Voice Response System (IVRS)/Interactive Web Response System (IWRS).

The investigator(s) will:

- 1 Obtain signed informed consent from the potential subject/parent or guardian of paediatric subject before any study specific procedures are performed.
- 2 Obtain a unique 7-digit enrolment number (E-code), through the IVRS/IWRS in the following format (ECCNNXXX: CC being the country code, NN being the centre number, and XXX being the subject enrolment code at the centre). This number is the subject's unique identifier and is used to identify the subject on the electronic case report forms (eCRFs).
- 3 Determine subject eligibility (see Section 5.1 and Section 5.2 for inclusion and exclusion criteria, respectively).

At Cycle 0 Day 1, once the subject is confirmed to be eligible, the investigator, or suitably trained delegate, will:

- 1. Call IVRS/IWRS for treatment assignment or registration.
- 2. Subjects may be enrolled but not treated. If the subject is not treated, the IVRS/IWRS should be contacted to terminate the subject in the system.
- 3. The IVRS/IWRS will be used to track drug supply.

Subjects may be rescreened once if the screening failure was due to a temporary condition. Any rescreening of subjects must be done in consultation with the AstraZeneca study physician and any decision must be captured in the subject's medical notes. If a subject withdraws from the study, then his/her enrolment code cannot be reused. Withdrawn subjects will not be replaced.

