8.1.3 Clinical outcome assessments (COAs)

COAs, an umbrella term referring to all outcomes and symptoms, can be reported directly by the subject (patient-reported outcomes), by a clinician (clinician-reported outcomes) or by an observer (observer-reported outcomes). In the current study, both patient-reported outcomes and observer-reported outcomes will be used. COA will be measured in accordance with Table 1. Copies of each of the assessments used are included in Appendix I.

Baseline clinical outcome assessments should be performed prior to and as close to the first dose of selumetinib as possible (PGIC should not have any baseline assessments). Post-baseline assessments should be performed at the end of each cycle up to the end of Cycle 4, every 2 cycles up to the end of Cycle 12, every 4 cycles up to the end of Cycle 24, and every 6 cycles thereafter, as long as the subject remains on study treatment. Clinical outcome assessments will be performed electronically using on-site tablets.

Clinical outcome evaluation questionnaire	Respondent	Relevant PN morbidity at enrolment	Age
FLACC	Parent/guardian-reported	All PN	3 years
Faces pain scale	Self-reported	All PN	4 to 17 years
NRS-11	Self-reported	All PN	Adults
PII	Self-reported Parent/guardian-reported	All PN	8 to 17 years Adults 5 to 17 years
Pain medication survey	Self-reported on paper in the adult cohort and Parent/guardian-reported on paper in the paediatric cohort	All PN	All subjects
PedsQL	Self-reported Parent/guardian-reported	All PN	5 to 7 years 8 to 12 years 13 to 17 years 3 to 4 years 5 to 7 years 8 to 12 years 13 to 17 years
EORTC QLQ-C30	QLQ-C30 Self-reported		Adults

Table 8Overview of eligible subjects completing clinical outcome
assessment questionnaires, by age of patient and respondent

CONFIDENTIAL AND PROPRIETARY

Clinical outcome evaluation questionnaire	Respondent	Relevant PN morbidity at enrolment	Age
PlexiQoL	Self-reported	All PN	Adults
PROMIS (mobility)	Self-reported Parent/guardian-reported	All PN	8 to 17 years 5 to 17 years
PROMIS (upper extremity function)	Self-reported Parent/guardian-reported	All PN	8 to 17 years 5 to 17 years
PROMIS (Physical Function – Short Form 8c 7-day)	Self-reported	All PN	Adults
PGIS	Self-reported Parent/guardian-reported	All PN	8 to 17 years Adults Up to 17 years
PGIC	Self-reported Parent/guardian-reported	All PN	8 to 17 years Adults Up to 17 years

Table 8Overview of eligible subjects completing clinical outcome

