8.1.3.1.3 NRS-11 (adult cohort only)

The NRS-11 is a self-reported segmented 11-point numeric scale that assesses pain intensity (Hawker et al 2011). It consists of a horizontal line with 0 representing "no pain" at the left end of the line and 10 representing "worst pain you can imagine" at the right end. Subjects are asked to select the one number from 0 to 10 that best describes their worst pain over the past 7 days for the following: 1) physician selected target-tumour pain, 2) overall tumour pain, and 3) overall pain. It takes less than 1 minute to complete. The target tumour will be selected by the physician from a list of body locations in Table 9. The NRS-11 is recommended as a core outcome measure of pain intensity for clinical studies (Dworkin et al 2005; Wolters et al 2013). Adult subjects only will complete the NRS-11 for this study.

1	Head	16	Pelvic area
2	Еуе	17	Genitalia
3	Face	18	Upper arm
4	Ear	19	Forearm
5	Mouth/Tough	20	Hand
6	Neck (Front)	21	Thigh/Upper leg
7	Neck (Back)	22	Lower leg
8	Shoulder	23	Foot
9	Chest		
10	Armpit		
11	Flank		
12	Back (Upper)		
13	Back (Lower)		
14	Abdomen		
15	Buttock		

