8.1.3.1.5 Pain medication survey (all subjects)

A pain medication survey will be used to ensure that potential pain palliation is not the result of increased usage of analgesics (Basch et al 2014). Information on daily and as-needed pain medications will be collected, including dates, pain medication name, dose and frequency. The pain medication survey will not be collected through the eCOA tablet, but with a paper version.

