6.	Has your child's pain affected your child's sleep?	0	1	2	3	4	5	6

Lab Matrix Form

Pain Interference Index - Adult

Below you will find a list of questions about you and your pain. Please answer each question by circling one number between 0 and 6.

Please note that we are asking about your situation during the past week.

Has	s your pain:	Not at	all		Son	ne		Completely
1.	made it difficult for you to work (in or outside the home)?	0	1	2	3	4	5	6
2.	made it difficult for you to do activities outside of work (leisure activities)?	0	1	2	3	4	5	6
3.	made it difficult for you to spend time with friends and family members?	0	1	2	3	4	5	6
4.	affected your mood?	0	1	2	3	4	5	6
5.	affected your ability to do physical activities (like run, walk up stairs, play sports, do chores)?	0	1	2	3	4	5	6
6.	affected your sleep?	0	1	2	3	4	5	6

Paticipant's ID:_____

Date:

Pain medication survey:

To be completed by the patient or patient care giver for all patients (all ages). Please collect daily and as needed pain medication for 1 week prior to randomisation Please include:

- Dates
- Pain medication name,dose and route
- Frequency

	Date:						
	//	//	//	//	//	//	///
#1 medication name,							
dosage, route							
#2 medication name,							
dosage, route							
#3 medication name,							
dosage, route							
#4 medication name,							
dosage, route							
#5 medication name,							
dosage, route							

.		11		1
l No	pain	medica	tions	used
	P			

completed by:

Date:

CONFIDENTIAL AND PROPRIETARY

140 of 183

Study Number: D1346C00011		Site Number:
Subject Number:	Visit Number:	Assesament Date:

ID#	
Date:	

PedsQL [™] Pediatric Quality of Life Inventory

Version 4.0

TEEN REPORT (ages 13-18) Acute Version

2		ECT	TIO.	ALC:
UI	ĸ		no	115

On the following page is a list of things that might be a problem for you. Please tell us how much of a problem each one has been for you during the past 7 days by circling:

> 0 if it is never a problem 1 if it is almost never a problem 2 if it is sometimes a problem 3 if it is often a problem 4 if it is always a problem

There are no right or wrong answers. If you do not understand a question, please ask for help.

PedsQL 4.0 - (13-18) Acute 03/00 Not to be reproduced without permission

Copyright C 1998 [name]. All rights reserved

PedsQL-Acute-Version-Adolescent_(Self Report)_V4.0_Orig_WS_Paper_English_US_03Sep2019_D1346C00011

Study Number: D1346C00011		Site Number:
Subject Number:	Visit Number:	Assessment Date:

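### The pain medication survey form anchors its recall week to a randomisation that this trial does not have, so the on-treatment forms, as written, do not ask for the week that the pain scores cover

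*Protocol*

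**What the plan says.** Section 8.1.3.1.5 gives the survey its purpose: "A pain medication survey will be used to ensure that potential pain palliation is not the result of increased usage of analgesics". It then lists the content: "Information on daily and as-needed pain medications will be collected, including dates, pain medication name, dose and frequency". It states no recall period.

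The form itself is in Appendix I. It is meant for patients of all ages, to be filled in by the patient or a caregiver, and its one time instruction is: "Please collect daily and as needed pain medication for 1 week prior to randomisation". Below that come seven columns with blank dates, and a date of completion.

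Section 6.3.1 states: "Randomisation will not be performed in this open label study".

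Table 1 lists the survey under footnote v ("Pain medication survey ^v"), with a baseline at Cycle 0 Day 1. The footnote sets the later frequency: "Post-baseline assessments should be performed at the end of each cycle up to the end of Cycle 4", then every 2 cycles to Cycle 12, every 4 to Cycle 24 and every 6 after that. Table 1 also marks the survey at end of treatment.

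On the status of the forms, Section 8.1.3 says: "Copies of each of the assessments used are included in Appendix I". The opening line of Appendix I instead describes them as illustrative examples.

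**The concern.** The form's only anchor is an event that does not occur in this trial. The nearest substitutes, enrolment or first dose, are fixed points before treatment. A respondent at the end of Cycle 8 who tries to follow the instruction must either report a pre-treatment week again or choose a window unaided.

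The trial is single-arm and open label, so a fall in pain score has no concurrent comparison. The survey is the safeguard that the protocol names against one obvious alternative explanation, namely that subjects took more pain medication. It is listed as an endpoint under the secondary pain objective, and the note below Table 6 in Section 6.5 says pain medication use will be analysed separately. To serve that purpose, the survey has to describe the same week as the pain score it is read against. An analysis plan cannot set the recall window once the forms have been completed.

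**Working it through.** The plan gives no figure to reproduce. The check is a comparison of texts and a count of visits.

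**1. Recall windows side by side**

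| Instrument | Window asked for at each visit | Source |
|---|---|---|
| NRS-11 (adults) | "best describes their worst pain over the past 7 days" | 8.1.3.1.3 |
| Pain Interference Index | the past week | 8.1.3.1.4, Appendix I |
| Faces scale (4 to 17 years) | the past week; today, if the child cannot recall the week | 8.1.3.1.2, Appendix I |
| FLACC (3 years) | none stated | 8.1.3.1.1, Appendix I |
| Pain medication survey | the week before randomisation | Appendix I |

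Three of the four pain instruments move with the visit. The survey is tied to one event, and that event does not happen.

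**2. How often the form is used** (Table 1, footnote v)

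- End of Cycles 1, 2, 3, 4: 4 visits
- End of Cycles 6, 8, 10, 12: 4 visits
- End of Cycles 16, 20, 24: 3 visits
- Total after baseline, to the end of Cycle 24: 4 + 4 + 3 = 11
- To the primary data cut-off (end of Cycle 10): Cycles 1, 2, 3, 4, 6, 8, 10 = 7

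With 32 subjects (16 + 16) all remaining on treatment, the scheduled forms number at most 11 × 32 = 352 to Cycle 24 and 7 × 32 = 224 to the primary cut-off. These are ceilings on forms scheduled, not counts of forms filled in wrongly. They leave out end-of-treatment forms and forms after Cycle 24.

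**3. Overlap if an anchor is supplied**

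Assumption, not in the protocol: randomisation is read as first dose, Cycle 0 Day 1.

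- Survey window: days −7 to −1.
- The end of cycle n falls on study day 2 + 28n. Check against Table 1: n = 1 gives 30, n = 12 gives 338, n = 24 gives 674. All three agree.
- First on-treatment pain week: visit on day 30, so days 23 to 29. With the −7 day visit window the visit falls on day 23, so the week starts on day 23 − 7 = 16 at the earliest.
- Days −7 to −1 and days 16 to 22 share no day, and every later visit is further away. The overlap is 0 days at all 11 visits. Under this reading only the baseline form matches its pain score.

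**4. Search for a correction elsewhere**

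Section 8.1.3.1.5 lists data items but no window. Footnote v fixes when the form is completed, not which days it covers. Section 8.1.3.6, on administration, does not address the survey's recall period. Nothing overrides the printed line.

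**The case against.** The case on the other side has five parts.

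- **The form in use may differ.** Appendix I labels its questionnaires as examples. This stands as a reason to confirm the wording first. It does not clear the point, because Section 8.1.3 calls the same forms copies and no other wording is given.
- **Context limits misreading.** A survey scheduled on treatment, in order to detect increased analgesic use, would make no sense if it recaptured a pre-treatment week, and Section 8.1.3.6 gives a named person at each centre responsibility for administering the assessments. Many sites may well enter the current week. But the instruction does not ask for that, so the window is left to each respondent or site.
- **Errors are visible.** The columns carry dates, so a wrong week can be seen and queried. This stands.
- **There is a parallel record.** Section 6.5 requires all medication, including over-the-counter products, to be recorded with reason, start and end dates, dose and frequency. This allows partial recovery. It may not show day-by-day as-needed use, which the seven columns are laid out to capture.
- **The week-matching argument is not universal.** FLACC states no recall period, and the Faces scale allows a same-day fallback. This stands and narrows the point.

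A reader might go further and infer that the change in analgesic use must come out as zero whatever subjects take, or that the pain results cannot be interpreted. The documents do not support either inference. Zero change needs a substitute anchor that the protocol does not supply, and needs respondents to reproduce the same pre-treatment week identically for up to two years. No change from baseline in analgesic use is defined in Sections 9.4.4.1 or 9.5.4.1. The dated columns and the concomitant-medication record remain available.

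**Conclusion.** The instruction is wrong as written. It names an event that Section 6.3.1 rules out, on a form repeated at 11 post-baseline visits to the end of Cycle 24 and beyond, and no section supplies another window. As printed, the on-treatment forms do not ask for the week covered by the NRS-11, the Pain Interference Index and the Faces scale. The probable consequence is inconsistent or wrong windows, which weakens the stated check on analgesic use but leaves it partly recoverable.

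Severity is minor to moderate. Pain is a secondary endpoint analysed descriptively, no hypothesis is tested (Section 9.1), and no sample size or error rate is affected. The conclusion assumes that the form used at sites carries the Appendix I wording, which the protocol leaves in doubt. The zero-overlap result also assumes that randomisation is read as first dose. The protocol does not show that any form was in fact completed for the wrong week.

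**What to change.** 1. Confirm the wording of the paper form in use. If it already carries a per-visit window, align Appendix I with it.
2. Otherwise replace the instruction with a request for pain medication taken in the 7 days before this visit, at every clinical outcome assessment visit. At baseline, ask for the 7 days before the first selumetinib dose. Both windows then end before the reference day.
3. State the same window in Section 8.1.3.1.5.
4. For forms already completed, check the entered dates. Where the wrong week was reported, use the dated concomitant-medication record from Section 6.5, and note that as-needed use may be incomplete there.

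The text change is one line on the form and one in Section 8.1.3.1.5, with no extra visit or data item. As a protocol amendment it needs ethics committee approval (Appendix A 1). Checking completed forms is additional data-management work, bounded by the ceiling of 352 scheduled post-baseline forms to Cycle 24, plus any end-of-treatment and later forms.

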Appendix K Abbreviations

Abbreviation or special term	Explanation
ADL	Activities of daily living
AE	Adverse event
ALP	Alkaline phosphatase
ALT	Alanine aminotransferase
AST	Aspartate aminotransferase
AUC	Area under the concentration-time curve from zero to infinity
AUC ₀₋₁₂	Area under the concentration-time curve from zero to 12 hours
AUC _{0-12,ss}	Area under the concentration-time curve from zero to 12 hours at steady state
AUC _{0-t}	Area under the concentration-time curve from zero to the last measurable concentration
BID	Twice daily
BOR	Best overall response
BP	Blood pressure
BSA	Body surface area
CFR	Code of Federal Regulations
CI	Confidence intervals
СК	Creatine kinase
C _{max}	Maximum plasma concentration
C _{max,ss}	Maximum steady-state plasma concentration
CR	Complete response
CSP	Clinical study protocol
CSR	Clinical study report
CTCAE	Common Terminology Criteria for Adverse Events
CV	Coefficient of variation
СҮР	Cytochrome P450
DCO	Data cut-off
DoR	Duration of response
ECG	Electrocardiogram
eCRF	Electronic case report form
EORTC QLQ-C30	European Organisation for Research and Treatment of Cancer Quality of Life Questionnaire Core 30
FLACC	Face, Legs, Activity, Cry, Consolability
GCP	Good Clinical Practice

CONFIDENTIAL AND PROPRIETARY

Abbreviation or special term	Explanation
GCV	Geometric coefficient of variation
G _{mean}	Geometric mean
HBsAg	Hepatitis B surface antigen
HBV	Hepatitis B virus
HCV	Hepatitis C virus
НСР	Health Care Professional
HL	Hy's Law
HRQoL	Health-related quality of life
IATA	International airline transportation association
ICF	Informed consent form
ICH	International Conference on Harmonisation
IEC	Independent Ethics Committee
IMMPACT	Initiative on Methods, Measurement, and Pain Assessment in Clinical Trials
IMP	Investigational medicinal product
International Co-coordinating investigator	If a study is conducted in several countries the International Co-coordinating Investigator is the investigator coordinating the investigators and/or activities internationally.
ІОР	Intraocular pressure
IP	Investigational product
IRB	Institutional Review Board
IVRS	Interactive voice response system
IWRS	Interactive web response system
LLN	Lower limit of normal
LLOQ	Lower limit of quantification
LVEF	Left ventricular ejection fraction
MEK	Mitogen activated protein kinase
MPNST	Malignant peripheral nerve sheath tumours
MRI	Magnetic resonance imaging
MUGA	Multigated acquisition
NCI	National Cancer Institute
NF1	Neurofibromatosis type 1
